6.2.2. Intensification of pharmacotherapy

The proportion of participants with an intensification of lipid-lowering pharmacotherapy will be determined from baseline and end-of-study prescription data, obtained from the CDW, medical record review, and patient surveys. Intensification of pharmacotherapy at 6-months will be a composite outcome including prescription of new monotherapy, dose escalation of existing pharmacotherapy, or addition of one or more medications to existing pharmacotherapy compared to baseline pharmacotherapy status.

6.3 Other prespecified outcomes

6.3.1. Medication adherence

Continuous medication adherence is assessed using medication possession ratios (MPRs) or proportion of days covered (PDC) as derived from CDW pharmacy data.⁶⁻⁸ All lipid-lowering related prescriptions, which are identified as active after the date of randomization and considered active either on or before the date 6 months from the date of randomization will be considered for analysis. PDC is calculated as the percentage of days in which a participant has access to a prescribed medication over the period of observation (assessed as sum of total days supply / total days in observation period). A measure of medication adherence is derived for each participant with a lipid-lowering medication prescription during the study observation period between the date of randomization and the date 6 months after randomization. Participants with a PDC of 80% or greater associated with lipid-lowering medications will be considered adherent. Total numbers of participants with lipid-lowering prescriptions, as well as subsets of participants with PDC measures will be reported in the final manuscript(s).

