4.3.2 End-of-study follow-up and period of observation

Enrolled participants will be observed for a total of 6 months. For the primary (change in LDL-C) and secondary (proportion meeting LDL-C targets) outcomes related to LDL-C, the end-of-study date will correspond to the date 6 months from the date of randomization. The most recent LDL-C value on or after this date, either associated with a completed study-related blood draw or LDL-C value extracted from CDW data (if unable to obtain an end-of-study specimen), will be used as the 6-month LDL-C value.

Similarly, for the secondary outcome associated with intensification of pharmacotherapy, the end-of-study date will correspond to the date 6 months from the date of randomization. All lipid-lowering related prescriptions, either derived from participant survey responses or extracted from CDW data, which are identified as active prior to or after the date of randomization and considered active either on or before the date 6 months from the date of randomization will be considered for analysis. Prescriptions are defined as active if they fall within a time window of one and a half times the total days supply (equivalent to a medication possession ratio of 0.67) from the prescription start date.⁶⁻⁸

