7.4 Other prespecified and exploratory outcomes

7.4.1 Medication adherence

Proportions of patients considered adherent to lipid-lowering medication prescriptions (PDC \geq 80%) are compared between the Immediate Results and Delayed Results arm using either a Z-test of proportions or chi-squared test. In the event of small cell counts, we will employ Fisher's exact test to ensure the validity of the results. We will compute the relative risk and 95% confidence intervals to quantify the strength and direction of the association.

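### The PDC formula in SAP 6.3.1 sums days of supply instead of counting covered days, so it can class participants as adherent at the 80% cut when far fewer days are covered

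*SAP*

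**What the plan says.** Section 6.3.1 opens by leaving the metric open: "Continuous medication adherence is assessed using medication possession ratios (MPRs) or proportion of days covered (PDC") from pharmacy data. It then defines one of the two in words: "PDC is calculated as the percentage of days in which a participant has access to a prescribed medication over the period of observation". A parenthesis in the same sentence gives the computation: "assessed as sum of total days supply / total days in observation period".

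The prescriptions that enter are pooled across drugs: "All lipid-lowering related prescriptions, which are identified as active after the date of randomization" and active by the 6-month date. The result is cut at one threshold: "Participants with a PDC of 80% or greater associated with lipid-lowering medications will be considered adherent". Section 7.4.1 compares the arms on this binary measure ("Proportions of patients considered adherent to lipid-lowering medication prescriptions") with a Z-test, chi-squared or Fisher's exact test and a relative risk.

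The window comes from section 4.3.2: "Enrolled participants will be observed for a total of 6 months". Section 6.3.1 states no cap at 100%, no rule for days on which supplies overlap, no rule for several drugs, and no rule for supply that crosses either end of the window.

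**The concern.** The words and the formula describe different quantities. A proportion of days covered counts days, so a day with two drugs on hand counts once and the maximum is 100%. A sum of days of supply over window length counts supply, so the same day can count twice and there is no maximum.

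The difference matters here because the prescriptions are pooled and because overlapping supply is an expected event. Section 6.2.2 counts "dose escalation of existing pharmacotherapy, or addition of one or more medications to existing pharmacotherapy" as intensification, and both can leave a participant with two supplies running at once. The value is then dichotomised at 80% and tested between arms, so an inflated ratio becomes a wrong class in a reported comparison. Two analysts, one following the words and one the parenthesis, could classify the same participant differently.

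**Working it through.** The SAP gives no expected adherence rate or power figure for this outcome, so there is no stated figure to reproduce. The check applies both definitions to the same fill histories.

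**Inputs**
- Window T = 182 days. This is an assumption, since the SAP says 6 months; calendar half-years run from 181 to 184 days.
- 90-day fills (assumed), with day 0 = randomization.
- Cut: 80% (section 6.3.1).

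**Formulas**
- As written in the parenthesis: S = (sum of days of supply) / T.
- As defined in words: C = (distinct days in the window with a drug on hand) / T.

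**Overlap inside the window** (no assumption about window edges needed)

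| Fill history | S | C | Class at 80% |
|---|---|---|---|
| One drug, fills on days 0 and 90 | 180/182 = 98.9% | 180/182 = 98.9% | same |
| Two drugs, one 90-day fill each on day 0 | 180/182 = 98.9% | 90/182 = 49.5% | differs |
| 90-day fill on day 0, replacement 90-day fill on day 30 | 180/182 = 98.9% | (30 + 90)/182 = 65.9% | differs |

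The third row treats the first supply as superseded by the replacement. It does not describe an early refill of the same drug that is used up later.

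**Supply crossing a window edge** (only if such supply is counted in full, which the SAP neither says nor excludes)

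| Fill history | S | C | Class at 80% |
|---|---|---|---|
| Fills on days 0 and 170 | 180/182 = 98.9% | (90 + 12)/182 = 56.0% | differs |
| Fills on days -80 and 60 | 180/182 = 98.9% | (10 + 90)/182 = 54.9% | differs |

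**Sensitivity to T.** With T = 181 or 184, S is 180/181 = 99.4% or 180/184 = 97.8%. The two-drug case has C = 90/181 = 49.7% or 90/184 = 48.9%. The replacement case has C = 120/181 = 66.3% or 120/184 = 65.2%. No class changes.

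**Does the error differ between arms?** An illustrative simulation gave everyone the same refill behaviour and varied only the share with an added drug. It used 90-day fills and random gaps between them, all assumed. The table shows the percentage at or above 80%.

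| Share with added drug | S, full supply | S, supply cut to window | C |
|---|---|---|---|
| 0% | 94.3 | 60.5 | 60.5 |
| 50% | 97.1 | 78.4 | 73.7 |

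The formula's excess over C with full supply is 94.3 - 60.5 = 33.8 points at 0% added and 97.1 - 73.7 = 23.4 points at 50%, so it falls. With supply cut to the window it is 0 and 78.4 - 73.7 = 4.7 points, so it rises. The direction of any between-arm distortion therefore turns on the unstated edge rule. With equal intensification in the two arms the error is equal.

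**The case against.** The strongest reply is that this is a loose parenthesis under an outcome that section 5.4 makes exploratory, and that for a single drug filled in sequence inside the window the two definitions agree. Both statements are true, and they limit the weight of the point. They do not remove it: the parenthesis is the only computation the SAP gives, and nothing elsewhere overrides it.

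Four stronger readings are tempting, and the SAP does not support them.

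- *The arms are misclassified differently.* A reader might infer this because section 3.2 anticipates escalation in the Immediate Results arm. But the SAP gives no adherence or add-on rate by arm and no escalation rate for the Delayed Results arm. The effect is conditional, with unknown size and sign.
- *The formula counts supply outside the window.* Section 6.3.1 is silent on this, and its words tie the measure to the observation period. The rule is missing; it is not stated wrongly. The 56.0% and 54.9% examples depend on that reading.
- *Late starters show the same error.* Someone who starts on day 60 and never misses a day scores 122/182 = 67.0% once supply is cut to the window, under words and formula alike, because both use the full period as denominator. That is a separate and debatable design choice.
- *Any value above 100% is a misclassification.* Two drugs with 180 and 90 days of supply give 270/182 = 148%, which is impossible for a proportion of days. Yet if the first drug covers 180 of 182 days the participant is above 80% either way.

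**Conclusion.** The point holds in a limited form. Section 6.3.1 states a formula that is not the quantity it defines. Followed as written, it can move participants above the 80% cut when supplies of concurrent or replaced drugs overlap: 98.9% against 49.5%, and 98.9% against 65.9%, in the two worked cases. These figures rest on an assumed 182-day window and assumed 90-day fills; the contradiction itself rests on the text alone.

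How many participants would be affected cannot be derived from the SAP, and neither can any between-arm bias. The consequence is confined to one prespecified but exploratory outcome. It is worth correcting before analysis because the present text fixes the wrong computation and leaves the metric open.

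**What to change.** In section 6.3.1:

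1. Replace the parenthetical formula with: the number of distinct calendar days in the observation window with at least one lipid-lowering drug on hand, divided by the number of days in the window (maximum 100%).
2. Count only supply that falls inside the window. State how supply carried in from before randomization and early refills of the same drug are placed on the calendar.
3. Use this single any-drug rule for the 80% cut, and delete the choice between the two metrics for the dichotomised outcome.

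Averaged drug-level PDCs could be a sensitivity analysis. They are a different measure: for drugs supplied for 180 and 90 of 182 days, the any-drug value is about 99% if the first drug's fills do not overlap, but the average is (98.9 + 49.5)/2 = 74.2%. They are worth adding because the any-drug value itself rises when a drug is added (60.5% to 73.7% at or above the cut in the simulation, with unchanged refill behaviour). A denominator starting at first fill could be another, with its limit noted: one 30-day fill with 30 days left scores 30/30 = 100%.

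The cost is a short wording change and a few lines of code on the same pharmacy data. No new data collection and no change to sample size are needed.

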5.0 Statistical Considerations

5.1 Statistical framework

The principal analysis uses an intention-to-treat (ITT)¹⁵ approach to compare the Immediate Results and Delayed Results arms. Using an independent t-test, analysis of the primary outcome uses a t-statistic, and two-sided type I error rate of 0.05 to test the null hypothesis of no difference in LDL-C change between arms. To quantify the treatment arm difference for the primary endpoint, a mean difference will be presented with a corresponding confidence interval estimate. Mean change in LDL-C is also reported separately for each arm. Similarly, for secondary and other pre-specified outcomes an ITT approach is used to make outcomes comparisons across treatment groups. Subset analyses, including sensitivity and group analyses by demographic, variant confirmation status, or other study or patient characteristics, are considered exploratory and will be described in detail if reported.

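### The adherence comparison, as Sections 6.3.1 and 7.4.1 read together, is conditional on having a prescription after randomization, so it is not the all-randomized ITT comparison the SAP describes

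*SAP*

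**What the plan says.** Section 6.3.1 sets out who receives an adherence value: "A measure of medication adherence is derived for each participant with a lipid-lowering medication prescription during the study observation period", where that period runs from randomization to 6 months. The prescriptions that count are those "identified as active after the date of randomization and considered active either on or before the date 6 months from the date of randomization", so a prescription first written after results are returned qualifies. PDC is "assessed as sum of total days supply / total days in observation period", and the binary outcome is defined by a threshold: "Participants with a PDC of 80% or greater associated with lipid-lowering medications will be considered adherent".

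Section 7.4.1 compares "Proportions of patients considered adherent to lipid-lowering medication prescriptions" between arms by a Z-test or chi-squared test (Fisher's exact test for small cells), with a relative risk and 95% confidence interval. It states no denominator.

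Section 5.1 says that "for secondary and other pre-specified outcomes an ITT approach is used to make outcomes comparisons across treatment groups". Adherence is listed among the other prespecified outcomes (Section 6.3), so the statement covers it. Section 4.4.1 defines the ITT population as everyone randomized, grouped by assigned arm. On the subset itself, Section 6.3.1 adds only a reporting commitment: "Total numbers of participants with lipid-lowering prescriptions, as well as subsets of participants with PDC measures will be reported".

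**The concern.** A participant without a prescription in the window has no adherence value and cannot enter the Section 7.4.1 test unless a further rule is written. Membership of the comparison is therefore decided after randomization, and the SAP expects the intervention to influence it, since a new monotherapy is a component of the intensification outcome in Section 6.2.2. Untreated participants who start a drug because they received their result enter the Immediate Results denominator. Their counterparts in the Delayed Results arm, who would have started had they been told, stay out.

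The two groups compared are then no longer balanced by randomization. If new starters reach the 80% threshold less or more often than people already on treatment, the arms differ even when nobody's adherence has changed. The planned relative risk and confidence interval could be read as a randomized effect of returning results on adherence.

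**Working it through.** The SAP gives no rate, power or sample size for adherence, so there is no stated figure to reproduce. The check has two parts.

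**1. The sections side by side**

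- Section 4.4.1: the ITT population is everyone randomized.
- Section 5.1: an ITT approach applies to other prespecified outcomes.
- Section 6.3.1: an adherence value exists only for those with a prescription after randomization.
- Section 7.4.1: arms are compared on the proportion adherent, with no denominator and no rule for those without a value.
- Section 6.2.2: a new monotherapy is part of a secondary outcome.

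The only denominator the text supplies is the one in Section 6.3.1, and it depends on an event that Section 6.2.2 treats as a possible result of the intervention.

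**2. How large the artefact could be (all rates assumed)**

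Let *p* be the share prescribed at baseline in both arms, *s* the share of the remainder who start in the Immediate Results arm (none in Delayed Results), *a* the share adherent among those already prescribed, identical in both arms, and *b* the share of starters reaching PDC ≥ 80%. Then:

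- Delayed rate = *a*
- Immediate rate = [*p·a* + (1 − *p*)*·s·b*] / [*p* + (1 − *p*)*·s*]
- Difference = *w*(*b* − *a*), where *w* = (1 − *p*)*·s* / [*p* + (1 − *p*)*·s*]

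The sign depends only on whether starters do better or worse than people already treated. The size depends on their share *w* of the Immediate denominator.

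First illustration: *p* = 0.70, *a* = 0.70, *b* = 0.40, with a further 15% of the Immediate arm starting (*s* = 0.15/0.30 = 0.50). The Immediate rate is (0.70 × 0.70 + 0.15 × 0.40)/(0.70 + 0.15) = 0.55/0.85 = 64.7%, against 70% in Delayed. The difference is −5.3 points, although no already-treated participant is affected.

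With *a* = 0.60 and a range of other values:

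| *p* | *s* | *b* | Immediate | Delayed | Difference (points) |
|---|---|---|---|---|---|
| 0.75 | 0.50 | 0.30 | 55.7% | 60% | −4.3 |
| 0.60 | 0.50 | 0.30 | 52.5% | 60% | −7.5 |
| 0.60 | 0.75 | 0 | 40.0% | 60% | −20.0 |
| 0.60 | 0.75 | 0.90 | 70.0% | 60% | +10.0 |
| 0.90 | 0.75 | 0 | 55.4% | 60% | −4.6 |
| 0.90 | 0.75 | 0.90 | 62.3% | 60% | +2.3 |

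Over *p* from 0.60 to 0.90, *s* from 0.25 to 0.75 and *b* from 0 to 0.90, the difference runs from −20 to +10 points. At *p* = 0.90 it stays between −4.6 and +2.3.

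The choice of denominator can reverse the sign. In the first row of the table, counting all randomized participants and treating the unprescribed as not adherent gives 0.75 × 0.60 + 0.125 × 0.30 = 48.75% against 45%, or +3.75 points instead of −4.3. That gain comes entirely from initiation.

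With the planned 122 per arm (Section 3.2) and *a* = 0.60, a simulation of 40,000 trials with a two-sided 0.05 Z-test rejected in about 9% (*p* = 0.75, *s* = 0.50, *b* = 0.30) and 16% (*p* = 0.60, otherwise the same). With *b* = 0 the figures were 23% and 50%; these are extreme cases.

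**The case against.** **The denominator is inferred.** A reader might conclude that the SAP openly restricts the test to prescribed participants and so flatly contradicts its ITT statement. The text does not go that far. Section 6.3.1 says who gets a value, Section 7.4.1 is silent on the denominator, and an ITT approach can be read as analysis by assigned arm. This stands as a limit on wording. It does not remove the problem: Section 4.4.1 defines ITT as all randomized, and no rule brings in those without a value.

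**Adherence to a drug never prescribed has no meaning.** Some restriction is natural, and the SAP promises to report subset sizes. Both are true. But a restriction fixed at randomization would serve equally well, and reporting counts discloses the selection without removing it. The SAP does not say that the counts will be given by arm.

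**The sizes are hypothetical.** This stands in full. The first illustration needs 30% untreated at baseline, half of them starting in one arm and none in the other, and starters much less adherent. At 122 per arm it would compare about 104 with 85 people, with a standard error near 7 points and *z* near 0.8, so that difference alone would not support a claim of effect.

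**Section 3.2 does not supply a start rate.** It is tempting to read its allowance for no escalation in up to 50% of the Immediate Results arm as implying that the other half enter the subset. Escalation under Section 6.2.2 also includes dose increases and add-on drugs in people already treated, which do not change who is in the denominator.

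**Little depends on this outcome.** Section 5.4 makes it exploratory, and Section 7.5 permits supplemental analyses.

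**Conclusion.** The point holds as a minor one. Followed as written, Sections 6.3.1 and 7.4.1 give a between-arm contrast conditional on a post-randomization event that the SAP itself counts as an intervention outcome. That contrast is not the all-randomized comparison of Sections 4.4.1 and 5.1, and it can mislead in either direction.

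The size cannot be established from the document. About 5 points is an illustration, not an estimate; the wider range of −20 to +10 points needs low baseline treatment and starters very unlike those already treated. If 90% or more are treated at baseline, the artefact is a few points at most under the assumptions used. All figures assume no new starts in the Delayed Results arm and identical adherence among those already prescribed.

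A reader might go further and infer that the trial's main result is compromised. The document does not support that: the LDL-C analysis does not use this subset, and no sample size rests on adherence.

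**What to change.** Amend Sections 6.3.1 and 7.4.1 along these lines:

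- *The between-arm comparison of adherence includes all participants with an active lipid-lowering prescription at randomization, analysed in the arm to which they were assigned. Those with no later fill during the 6 months are counted as PDC = 0.* The second sentence is needed because dropping people who never refill would bring back post-randomization selection.
- Define active at randomization from CDW pharmacy data with the rule in Section 4.3.2. Section 4.5 also draws baseline therapy from the survey, but PDC comes from CDW alone, so a participant known to be treated only from the survey would be scored zero for lack of data.
- Report adherence in new starters descriptively, by arm, with numbers.
- Label any comparison restricted to participants with a post-randomization prescription as descriptive and non-ITT, and note this exception in Section 5.1.
- If an all-randomized analysis with PDC = 0 for the unprescribed is added, label it as combining initiation with adherence. Initiation is already captured by the intensification outcome.

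The cost is SAP wording; no new data are needed. The main adherence comparison will have somewhat fewer participants and will answer a narrower question: whether returning results changes adherence among people already treated.

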6.3.2. Cascade testing

The number of first-degree relatives undergoing genetic testing within 6 months will be recorded for each participant, as measured on the end-of-study survey.

6.3.3. Self-reported quality of life

Self-reported quality of life is assessed via the baseline and end-of-study surveys, using the Veterans RAND 12-Item Health Survey (VR-12).¹⁰⁻¹² The VR-12 computes two continuous composite scores, a physical component summary (PCS) and a mental component summary (MCS).

6.3.4. Lifestyle behaviors

Lifestyle behaviors are assessed using items structured on the transtheoretical model of behavior change.¹⁹ Response options seek to assess at what point participants are in the behavior change process at 6 months. Response options assess readiness for change across myriad lifestyle behaviors using response options ranging from engaging in a specific behavior for more than 6 months (maintenance stage) to not at all (precontemplation stage).

a) Self-reported physical activity²⁰

Self-reported physical activity is assessed with the baseline and end-of-study surveys, using the single-item question “Do you exercise 3 times a week for at least 20 minutes each time?”

b) Self-reported smoking status^{21,22}

Self-reported smoking status is assessed with the baseline and end-of-study surveys, using two items: “Are you currently a smoker?” and, if yes, “Are you seriously thinking of quitting smoking?”

c) Self-reported saturated fat consumption¹⁹

Self-reported saturated fat consumption is assessed with the baseline and end-of-study surveys, using the single-item question “Do you consistently avoid eating high fat foods?”

